8.2. Secondary Analysis

The secondary analysis in this study aims to estimate effect of SB-FIX infusion on bleeding episodes and AAV2/6 SB-FIX recombinant related assessments.

8.2.1. FIX antigen and FIX activity levels

The FIX antigen and FIX activity levels are assessed over time during the study. The level of FIX antigen and FIX activity will be summarized by treatment cohort and by visit for baseline, post-baseline and change from baseline values. Corresponding listing will be provided. The mean and standard error by cohort will be plotted for each parameter by timepoint and treatment cohort.

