If FIX activity of a subject reaches  $\geq 5\%$  post infusion (2 measurements at least one week apart), investigator will consult with Medical Monitor to discontinue prophylactic FIX treatment and agree an appropriate monitoring regimen.

At each study visit, laboratory blood tests, assessment of AEs, concomitant medications, and frequency of bleeding episodes and FIX usage will be performed ([Appendix 1](#)).

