### **4.2 Exclusion Criteria**

Subjects who meet any of the following criteria will be excluded from participating in the study:

1. Presence of neutralizing antibodies to AAV2/6
2. History of hypersensitivity response or an allergic reaction to FIX or FIX products
3. Currently receiving long acting FIX replacement therapy and unwilling to switch to short acting FIX infusion
4. FIX mutations known to be associated with FIX inhibitors, including those with a large gene deletion
5. Polymorphisms in the ZFN target region of the albumin locus
6. Presence of any liver mass on MRI or equivalent imaging technology, or elevated alpha-fetoprotein (AFP)
7. Any contraindication to the use of corticosteroids for immunosuppression
8. Currently receiving antiviral therapy for hepatitis B or C or with history of active hepatitis B (HBV DNA or HB Ag positive) or hepatitis C (HCV RNA viral load) or HIV-1 (RNA viral load) or HIV1/2 antibody positive. To be considered HCV-negative after treatment of an active HCV infection, viral assays in two samples, collected at least six months apart, must be negative.
9. Chronic anemia, leukopenia, or thrombocytopenia
10. Past medical history of active tuberculosis or significant fungal disease
11. Symptomatic cardiovascular disease as a co-morbid condition
12. Markers of hepatic inflammation or overt or occult cirrhosis as evidenced by one or more

of the following:

- a. Albumin  $\leq 3.5$  g/dL (35 g/L)
  - b. Total bilirubin  $> 1.5$  x ULN and direct bilirubin  $\geq 0.5$  mg/dL (8.55  $\mu$ mol/L)
  - c. Alkaline phosphatase  $> 2.0$  x ULN
  - d. ALT or AST  $> 2.0$  x ULN
13. History of chronic renal disease or creatinine  $\geq 1.5$  mg/dL (133  $\mu$ mol/L)
  14. Systemic (iv or oral) immunomodulatory agent or steroid use (topical treatment is allowed, e.g., for asthma or eczema) within 3 months prior to Screening
  15. History of chronic infection or other chronic disorder considered an unacceptable risk
  16. History of malignancy except for treated basal cell or squamous cell carcinoma
  17. History of alcohol or substance abuse
  18. Previously received gene therapy product
  19. Participation in prior investigational drug or medical device study within the previous 3 months
  20. History of therapeutic non-adherence
  21. Any other reason that, in the opinion of the Investigator or Medical Monitor, would render the subject unsuitable for participation in the study

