## **6 STUDY METHODOLOGY**

Prior to initiation of this study, this study site shall be approved by the local Institutional Review Board (IRB) or EC equivalent. Subjects must be willing to participate in all study procedures related to this protocol. The following sections describe all study procedures. Additional detailed instructions will be provided in the Study Reference Manual. A table of all study procedures is presented in the Schedule of Events ([Appendix 1](#)).

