### **6.1 Screening Visits**

The objective of the screening visits is to identify subjects who meet the stated inclusion and exclusion criteria and who are willing and able to participate in the study. Screening evaluation may take up to approximately 3 months and may be performed across several visits during the screening period. Assessments must be completed and the results reviewed to judge and confirm eligibility. The following will be performed at the screening visits:

1. Obtain a signed and dated subject informed consent form and authorization document to use and disclose medical information prior to performing any study-specific procedures
2. A complete medical history including demographic information; access and review of concomitant medications. If the subject is not normally seen at the study center, it may be necessary to obtain medical records to confirm study eligibility.
3. Vital signs: Temperature, pulse, respiratory rate, and blood pressure
4. Review the inclusion and exclusion criteria

5. Assign a subject number
6. Physical exam, including height
  - a. Physical exam includes assessments of skin, head, eyes, ears, nose, throat, respiratory, cardiovascular, gastrointestinal, endocrine metabolic, genitourinary, neurological, lymphatic and musculoskeletal systems.
7. Weight
8. 12-lead ECG
9. Chest X-ray
10. Urinalysis with microscopic exam
11. CBC with differential and platelet count
12. Coagulation screen: PT, INR, and PTT
13. Chemistry (Na, K, Ca, HCO3, Cl, and phosphorus)
14. Metabolic panel (BUN, creatinine, glucose, uric acid)
15. Liver panel (total and direct bilirubin, alkaline phosphatase, ALT, AST, LDH, albumin, and total protein). Two liver panel tests should be performed at least one week apart during Screening. Note: direct bilirubin is performed at Screening only.
16. Neutralizing antibodies to AAV2/6
17. HBV DNA, Hepatitis B Surface Antigen, HCV RNA viral load, and HIV RNA viral load; HIV-1/2 antibody assay
18. FIX antigen and activity levels
19. FIX inhibitor level
20. SNP assay for the ZFN targeted region of the albumin locus
21. Assessment of concomitant medications
22. FIX genome sequencing (if not performed previously)
23. Liver MRI or equivalent imaging technology
24. Circulating alpha fetoprotein level

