## 7.2 Concomitant Medication and Supportive Care

The investigator will record all concomitant medications including those given in treatment of AEs on the concomitant medication page in the subject's case report form. Any medication taken by the subject from screening throughout the course of the study, including over-the-counter medicinal products, dietary supplements, and herbal medications, should be recorded on this form. A short course of prednisone (or equivalent) may be instituted either as prophylaxis or post AAV exposure if an immune reaction to the AAV capsid develops (See [Appendix 3](#)). Any treatment with prednisone (or equivalent) and pre-treatment with acetaminophen and diphenhydramine hydrochloride should be recorded on the concomitant medications page.

All medications including Factor IX short acting are permitted with the exception of those that are potentially hepatotoxic. Hepatotoxic agents such as diclofenac, amiodarone, chlorpromazine, fluconazole, isoniazid, rifampin, valproic acid, high doses of acetaminophen (4-8 gm/day) are not permitted.

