3.2.2. Secondary Endpoints

- Changes in FIX antigen and FIX activity levels from baseline over time
- Change from baseline in the number of FIX units infused per week
- Change from baseline in number and severity of bleeding episodes
- Changes in neutralizing antibodies to FIX from baseline over time
- Presence and shedding of AAV2/6 vector DNA, by PCR in plasma, saliva, urine, stool and semen over time

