3.4. Dose Modifications

No dose modifications are possible within an individual subject as this is a single infusion study.

4. General Statistical Considerations

Study day will be calculated as event/assessment date - date of SB-FIX infusion. Thus, the date of SB-FIX infusion is considered as Day 0. The relative study day for assessment will be derived as the assessment date subtracted from the date at Day 0.

Baseline is defined as the last non-missing assessment prior to the SB-FIX infusion. Measurements that are obtained after infusion will be considered as post-baseline values. Change from baseline is defined as post-baseline assessment minus baseline assessment.

Summary tables will be provided when there is more than one enrolled subject in a cohort. Otherwise, data will be presented in the form of a listing.

Continuous variables will be summarized using the following descriptive statistics: the number of subjects (n), mean, standard deviation (SD), median, minimum and maximum,

where appropriate. Categorical variables will be summarized using the frequency count (n) and percentage (%) of subjects for each category, where appropriate.

No imputation will be performed for missing data unless otherwise specified.

Data will be displayed in all listings sorted by treatment cohort and subject identifier.

All analyses will be conducted using SAS[®] Version 9.3 or higher. The Medical Dictionary for Regulatory Activities (MedDRA) version 23.0 will be used for coding adverse events. Prior or concomitant medication data will be coded using the World Health Organization (WHO) Drug Dictionary Global B3 March 2020.

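### SAP 8.2.1 summarises FIX levels and change from baseline without showing how recently each sample followed FIX concentrate

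*SAP*

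**What the plan says.** Change in FIX level is the first-listed secondary endpoint in SAP 3.2.2: "Changes in FIX antigen and FIX activity levels from baseline over time". SAP 8.2.1 gives the analysis: "The level of FIX antigen and FIX activity will be summarized by treatment cohort and by visit for baseline, post-baseline and change from baseline" values, with a listing and a plot of cohort means and standard errors. SAP Section 4 sets the reference value: "Baseline is defined as the last non-missing assessment prior to the SB-FIX infusion". It attaches no condition about recent FIX concentrate.

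Protocol 7.2 allows concentrate during the study: "All medications including Factor IX short acting are permitted with the exception of those that are potentially hepatotoxic". Under Protocol 3.6, once activity is at least 5% on two measurements a week or more apart, the "investigator will consult with Medical Monitor to discontinue prophylactic FIX treatment". Prophylaxis may therefore be running when the baseline sample and many later samples are drawn. Protocol 4.2 excludes a subject who is "Currently receiving long acting FIX replacement therapy and unwilling to switch to short acting FIX infusion".

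The visit lists (Protocol 6.1 to 6.10) and Appendix 1 name the FIX tests without relating them to the last infusion; the Protocol 6.1 entry, for example, reads only "FIX antigen and activity levels". Protocol 6 does add: "Additional detailed instructions will be provided in the Study Reference Manual". That manual was not among the documents reviewed.

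**The concern.** A plasma FIX assay measures whatever FIX is circulating. If concentrate is still present, the value is transgene FIX plus residual concentrate, and SAP 8.2.1 treats the whole as the study result. Residual in a post-baseline sample raises both the reported level and the change. Residual in the baseline sample lowers the change.

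The analysis is descriptive, so no test or error rate is at risk. What is at risk is the reading of the tables and plots. Cohorts start at two adults, so one subject's artefact carries half the weight of the cohort mean. The data needed to spot affected samples are largely collected: a diary of factor infusions from the baseline visit (Protocol 6.3) and a record of all medication from screening (Protocol 7.2). However, SAP 8.2.2 uses factor data only for per-subject counts and annualised frequencies. No display places an infusion time beside a FIX value.

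**Working it through.** **Inputs from the documents.** Native activity below 1% (Protocol 4.1); weekly activity draws in Weeks 2 to 12 (Protocol 6.7); two adults per starting cohort (SAP 3.1).

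**Inputs assumed, because the documents give none.** Peak rise after a dose 20, 30, 40, 50 or 60% of normal; half-life 12, 18, 24 or 30 h; concentrate every 84 h; carry-over from earlier doses ignored.

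**Direction.** Observed change = true change + post-baseline residual − baseline residual. For illustration, take a true rise of 5 points:
- residual of 5 post-baseline only: 5 + 5 − 0 = 10 (overstated);
- residual of 5 at baseline only: 5 + 0 − 5 = 0 (effect hidden);
- residual of 10 at baseline only: 5 + 0 − 10 = −5 (apparent fall);
- residual of 5 at both: 5 + 5 − 5 = 5 (change correct, post-baseline level overstated by 5).

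**Residual per sample.** Residual(t) = peak × 2^(−t/half-life). The lowest value uses peak 20% and half-life 12 h; the highest uses 60% and 30 h.

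| Hours since infusion | Lowest | Highest |
|---|---|---|
| 24 | 20 × 2^(−2) = 5.0% | 60 × 2^(−0.8) = 34.5% |
| 48 | 20 × 2^(−4) = 1.3% | 60 × 2^(−1.6) = 19.8% |
| 72 | 20 × 2^(−6) = 0.3% | 60 × 2^(−2.4) = 11.4% |

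**Average inflation of a level.** For draws uniform over 0–84 h, mean residual = peak × half-life / (84 × ln 2) × (1 − 2^(−84/half-life)). The lowest is 20 × 12 / 58.2 × 0.992 = 4.1 points and the highest 60 × 30 / 58.2 × 0.856 = 26.5 points.

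**Scatter in change, no transgene FIX, subject on prophylaxis throughout.** One million baseline/post-baseline pairs were simulated at each of the 20 peak and half-life combinations. In the middle row, the baseline draw is uniform over the cycle and the later draw falls within 6 h of the same point in it.

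| Draw timing | Rise of ≥5 points | Fall of ≥5 points |
|---|---|---|
| Independent, uniform over 0–84 h | 19–39% | 19–39% |
| Phase varies by ±6 h | 2–8% | 2–8% |
| All draws at 60–84 h | 0–2% | 0–2% |

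Mean change is about 0 in every row, so this is scatter and not bias. The SD of change is 6.8–21.8 points in the first row and 0.2–2.6 in the last. For a two-subject mean, the first-row SD becomes 6.8/√2 = 4.8 to 21.8/√2 = 15.4. A single 5-point artefact moves that mean by 5/2 = 2.5.

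**The case against.** The strongest reply is that the design already limits the problem. Two 84 h intervals make exactly one week (2 × 84 = 168 h), so weekly draws on a fixed weekday meet the same point of the dosing cycle and the residuals largely cancel in the change. That stands for Weeks 2 to 12 and is why the middle row above is much smaller than the first. Visit windows of ±3 days, and later ±1 week, can loosen the alignment. Cancellation also does nothing for the reported levels.

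Next, every subject has native activity below 1%, and SAP 8.2.1 tabulates baseline. A baseline activity clearly above 1% therefore reveals residual concentrate. This stands, so a reader who inferred that the displays contain no clue would be wrong. It does not expose post-baseline inflation. It does not serve for antigen, because Protocol 4.1 admits subjects with cross-reactive material.

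FIX values and concomitant medications are listed, and with few subjects they could be compared by hand. That works only if infusion clock times are recorded, which the documents do not state. The exclusion concerning long-acting products shortens carry-over without removing it. The unseen manual may time the draws, but that alone would not put a flag in the SAP, and concentrate given for a bleed could still precede a draw.

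Finally, this is a descriptive Phase 1 study and FIX level is a secondary endpoint. That lowers the stakes, and the point is rated accordingly.

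**Conclusion.** The omission is real, and closing it is a cheap improvement. Following the SAP exactly pools samples containing concentrate with samples free of it. The direction needs no pharmacokinetic assumption: post-baseline levels are inflated while concentrate is on board; change is biased downward when a subject stops after a baseline drawn on it, and upward when concentrate is present only post-baseline; otherwise the effect on change is mainly symmetric scatter. The size ranges from negligible to large, depending on peak, half-life and draw timing, all assumed here. Subjects not using concentrate are unaffected.

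Three stronger readings are not supported.
- A reader might infer that the analysis systematically favours SB-FIX. On a stable regimen rises and falls are equally likely, and the responder who stops concentrate is biased against SB-FIX.
- A reader might infer that the artefact is shown to exceed the expected effect. Protocol 1.7 offers no firm benchmark: its 290 ng/mL (5.8% at 50 ng/mL per 1%) accompanies text naming a top dose of 2E+13 vg/kg, whereas the upper cohort is 5E+13. Other values require extrapolating an approximate primate dose-response.
- A reader might infer that protocol rules that use a FIX level need changing. No contradiction between passages is shown here, and no clinical rule is in question.

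**What to change.** In SAP 8.2.1:
1. Derive time since the last FIX infusion for every activity and antigen sample, baseline included, from the diary and the concomitant medication record. Record the clock time of the last infusion where it is not already captured. List the interval beside each value.
2. Flag samples drawn within an interval that the sponsor prespecifies from product pharmacokinetics.
3. Keep the all-values summary and plot, with flagged values marked. Add a supportive summary of levels and change restricted to unflagged samples, taking the last unflagged pre-infusion value as baseline. Show the number of evaluable subjects and on/off prophylaxis status at each visit.
4. State that the restricted summary is supportive only, because it may over-represent subjects who stopped concentrate, and that a subject with no unflagged baseline contributes levels but not change.

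The cost is at most one added data item, one flag and extra displays, with no extra visits, draws or subjects. The drawback is sparse data for subjects on regular prophylaxis. With draws uniform over 84 h, an illustrative 48 h limit leaves (84 − 48)/84 = 43% of samples unflagged, and a 72 h limit (84 − 72)/84 = 14%. With one draw at Screening and one at Baseline, independently timed, (48/84)² = 33% or (72/84)² = 73% of such subjects would have no unflagged baseline. If both draws fell at the same point of the cycle, the shares would be 48/84 = 57% and 72/84 = 86%. The restricted summary should therefore accompany the all-values summary and not replace it. No protocol clinical rule changes.

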8.2.2. Bleeding episodes and Factor replacements

The bleeding episodes and FIX concentrates usage is recorded in diary over time during the study. The subjects will report the bleeding episodes at each visit. The severity has three levels: mild, moderate and severe. The related information of each bleeding episode will be presented in a listing. The number of bleeding episodes and Factor replacements usage after three weeks post treatment will be summarized by subject. In addition, the corresponding annualized frequency will be calculated at subject level too. Factor replacements include Benefix, Ixinity, and Mononine. The annualized bleeding episodes will be derived as

*Annualize Number of Bleeding Episodes \geq 3 Weeks = (Number of Bleeding Episodes \geq 3 Weeks) / (Post Dose Days at Last Visit - 21 Days) * 365.25*

and the number of Factor replacement exposed will be annualized in same approach.

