### **12.5.2 Secondary Endpoints**

Secondary endpoints include:

1. Changes in FIX antigen and activity levels from baseline over time
2. Change from baseline in the number of FIX units infused per week
3. Change from baseline in number and severity of bleeding episodes
4. Changes in neutralizing antibody to FIX from baseline over time
5. Presence and shedding in AAV2/6 vector DNA, by PCR in plasma, saliva, urine, stool and semen over time

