8.2.3. Neutralizing Antibodies to FIX

FIX inhibitor level reflects the immunogenicity response to FIX. It is collected over time during the study. The level of FIX inhibitor will be summarized by treatment cohort and by visit for baseline, post-baseline and change from baseline values. Corresponding listing will be provided. The mean and standard error by cohort will be plotted by timepoint and treatment cohort.

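### SAP 8.2.2 does not produce the bleeding and FIX-use endpoints as defined: no pre-infusion value, no change, no stated unit for FIX use, no severity summary

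*SAP*

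**What the plan says.** The FIX-use endpoint in Protocol 12.5.2 is "Change from baseline in the number of FIX units infused per week". The bleeding endpoint in SAP 3.2.2 is "Change from baseline in number and severity of bleeding episodes". Both documents carry both endpoints in the same words.

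SAP 8.2.2 sets out the analysis: "The number of bleeding episodes and Factor replacements usage after three weeks post treatment will be summarized by subject". It adds a subject-level annualised frequency for bleeds: the count from week 3 on, divided by days from infusion to last visit less 21, times 365.25. For factor use it says that "the number of Factor replacement exposed will be annualized in same approach". It names three severity levels and then says "The related information of each bleeding episode will be presented in a listing".

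The sections on either side do more. SAP 8.2.1 says that "FIX activity will be summarized by treatment cohort and by visit for baseline, post-baseline and change from baseline values", and SAP 8.2.3 says "The level of FIX inhibitor will be summarized by treatment cohort and by visit for baseline, post-baseline and change from baseline values".

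The general rule in SAP Section 4 is "Baseline is defined as the last non-missing assessment prior to the SB-FIX infusion".

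Pre-infusion data are collected. Bleeding and FIX usage are assessed at the baseline visit (Protocol 6.3) and before infusion on Day 0 (Protocol 6.4). The diary of bleeds and factor infusions starts at the baseline visit, at most 21 days before infusion (Protocol 6.3). Medications are recorded from screening (Protocol 7.2, SAP 7.1), which may last about three months (Protocol 6.1).

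**The concern.** An endpoint defined as a change needs a value before treatment, a value after it, and their difference. SAP 8.2.2 plans only the value after. In a study without a control arm, a subject's own pre-infusion experience is the natural reference for his bleeding and factor use, and a post-infusion rate alone says nothing about change.

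Three gaps add to this. FIX use has no stated unit and no weekly basis, although the endpoint has both. Severity is half of the bleeding endpoint but has no specified summary. No counting period is given for a baseline rate, so anyone who adds a baseline later must choose its window and source with the data in hand.

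**Working it through.** No power, alpha or sample-size figure bears on this point, and the plan states no numerical result to reproduce. The check compares definition with analysis and then runs the SAP's own formula.

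**1. Definition against planned output**

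| Element of the endpoint | Defined in Protocol 12.5.2 and SAP 3.2.2 | Planned in SAP 8.2.2 |
|---|---|---|
| Change from baseline | Yes, both endpoints | No pre-infusion value, no difference |
| FIX use in units | Yes | Unit not stated |
| FIX use per week | Yes | Annualised quantity; no weekly figure |
| Number of bleeds | Yes | From week 3 after infusion only |
| Severity of bleeds | Yes | Listing only |

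**2. Can the general rule in SAP Section 4 supply the baseline?** It selects the last assessment before infusion. Read literally, that is the Day 0 assessment, and neither document says what period it covers. A bleed rate or weekly FIX amount needs a count and a number of days; the rule gives no days.

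**3. The SAP formula with different baselines.** Assumed: one bleed from week 3, last visit at day 365.

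Rate = 1 / (365 − 21) × 365.25 = 1.06 per year.

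The change would be +1.06, −1.94, −10.04 or −46.94 per year for pre-infusion rates of 0, 3.0, 11.1 or 48. These rates appear in, or lie within ranges reported in, the summaries of other trials in Protocol 1.2. The planned output is 1.06 in all four cases.

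**4. The same formula for factor use, if the annualised quantity is a count of infusions.** Assumed: 98 infusions from week 3 to day 365.

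Annualised count = 98 / 344 × 365.25 = 104.05.

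IU per week = 98 × (IU per infusion) / (344 / 7). At assumed sizes of 1,000, 2,000 and 4,000 IU this gives about 1,994, 3,988 and 7,977. One annualised count fits a fourfold range of the quantity that the endpoint names.

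**5. How good would a diary baseline for bleeds be?** Inputs: 11.1 bleeds per year, a pre-treatment mean from another trial cited in Protocol 1.2 (individual range 0 to 48); Poisson counts; a 21-day window (the maximum) and a 7-day window (illustrative).

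- 21 days: expected bleeds = 11.1 × 21 / 365.25 = 0.64; probability of none = exp(−0.638) = 53%.
- 7 days: expected bleeds = 11.1 × 7 / 365.25 = 0.21; probability of none = exp(−0.213) = 81%.
- One bleed in 21 days annualises to 365.25 / 21 = 17.4 per year.

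A subject with no diary bleed before infusion has a baseline of zero, so he can show only no change or worsening. The 21-day figure is a best case: many windows will be shorter, and variation between subjects raises the share with none above the single-rate figure.

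**The case against.** The strongest reply is that the defaults fill the gap. Protocol 12.5.3 says the endpoints will be summarised descriptively, the endpoints are defined as changes, and bleeding and FIX usage are assessed at Baseline and Day 0, so the last-assessment rule has something to select. It is true that an assessment exists. It remains unclear what period it counts, and without one neither a rate nor a weekly amount can be formed. Default category counts might yield a post-infusion severity table, but not a change.

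Second, pre-infusion data would reach the listings: bleeds through SAP 8.2.2, and FIX use through SAP 7.1 where it is recorded as a medication. With at most 16 subjects, a reader could reconstruct something by hand. This reduces the harm, but it leaves the reader to choose the window and produces no summary of the endpoint.

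Third, a change in bleed rate from a diary of at most 21 days could mislead. This stands. It is a reason to show raw counts and days observed and to state the weakness, not to leave a defined endpoint without its baseline.

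Three stronger readings are tempting, and the documents do not support them:

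- A reader might infer that the SAP has replaced FIX units by a count of infusions. SAP 8.2.2 also speaks of usage, and its phrase about factor replacement exposed could mean infusions, exposure days or amount. The supportable statement is that the unit is not given.
- A reader might infer that the omission spoils a comparison of the two dose cohorts. SAP 8.2.2 summarises these data by subject and proposes no such comparison. The cohorts are sequential, non-randomised and start with two adults each, so a baseline would not make them comparable.
- A reader might infer that adverse events recorded from consent give a longer bleed baseline. Protocol 9.1.1 counts a pre-existing condition as an adverse event only if it worsens, and Appendix 1 marks no adverse event assessment at Screening.

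**Conclusion.** The point holds. Followed as written, SAP 8.2.2 does not produce two of the five secondary endpoints as both documents define them. This rests on the text alone. The numerical examples show only what the planned output cannot distinguish, and they use assumed counts and infusion sizes.

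The defect should be fixed but is not critical. SAP Section 1 rules out hypothesis testing, and no escalation or stopping rule uses bleed counts or FIX use. The bleed baseline will be weak per subject even after correction: 53% with no recorded bleed at 21 days and 81% at 7 days, assuming Poisson counts and a rate of 11.1 per year borrowed from another trial. A change in bleed rate should therefore be read as descriptive only.

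**What to change.** In SAP 8.2.2:

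1. Name a pre-infusion window and data source for each endpoint, from data already collected: the diary from the baseline visit for bleeds, and the diary or the medication records from screening for FIX use. State that this replaces the last-assessment rule for these two endpoints.
2. Express FIX use as IU per week before and after infusion, and report the within-subject change. If IU per infusion is not captured, say so and say what can be reported instead.
3. Report bleeds before and after infusion, by severity, with the change. Show raw counts and days observed beside any annualised rate.
4. State that the diary baseline for bleeds covers at most 21 days and is weak for an individual subject.

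The cost is SAP wording and a little more programming, with no new data collection. The documents do not state whether the diary or medication page records IU per infusion, so item 2 depends on checking that. The downside is an imprecise bleed baseline, which items 3 and 4 make visible.
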